6.1.3 Medical history

Medical history will be summarized by MedDRA body system organ class (SOC) and preferred term (PT) for the ITT population overall, by treatment group, and for pooled arms A & C.

6.1.4 Extent of Exposure

Extent of exposure will be summarized for the Safety population by treatment group, using descriptive statistics.

- Duration of study treatment will be calculated in days as the date of the last dose of study – date of the first dose of study treatment + 1
- Number of radium-223 dichloride injections received. Summary statistics will include both descriptive statistics of number of doses received, and number and percent of subjects by number of doses received
- Total activity of radium-223 dichloride (sum of activity in all doses) in kBq and kBq/kg
- Dose intensity of radium-223 dichloride calculated as total activity of radium-223 dichloride/(duration of study treatment + 27), in kBq/day and KBq/kg/day
- Number and percent of subjects with dose modifications (none, at least one interruption/delay)
- Normalized dose for total body weight (TBW) and ideal body weight (IBW) will be summarized by quartile:

Total body weight normalized dose=Activity in the first dose administered to subject /body weight used for first dose

Ideal body weight normalized dose= Activity in the first dose administered to subject /ideal body weight

All exposure summaries will be based on the old standard (50 or 80 kBq/kg). Hence, doses administered with the new standard (55 or 88 kBq/kg) will be converted to the old standard prior to any analyses as specified below. A country specific 2016 NIST implementation date will be utilized for this conversion.

Radioactivity will be calculated as follows:

- Activity per injection (kBq) = Activity in syringe before injection (kBq) - activity in syringe after injection (kBq)
- Activity adjusted
 1. If the dose date is prior to 2016 global NIST implementation date in the country, then Activity per injection = Activity per injection

2. If the dose date is after the 2016 global NIST implementation date in the country, then Activity per injection = Activity per injection/1.1

- Total activity injected (kBq) = Sum of ('Activity per injection')

6.1.5 Prior and Concomitant Medications

All investigator-reported non-study medications taken before and/or during the study will be coded using the Bayer modified version of World Health Organization Drug Dictionary (WHO-DD) 2005 Q3 and the Anatomical Therapeutic Chemical (ATC) classification system. Coding will include the drug class and generic drug name.

Non-study medications taken before and/or during the study will be categorized as prior medications, concomitant medications, and post treatment medications.

Classifications of prior and concomitant medication as based on [Table 6–1](#).

If a start date is missing, the medication will be assumed to start prior to first dose of study drug. If the end date is unknown and 'ongoing' was not checked in CRF, the medication will be assumed to end at the last visit date, death date or withdrawal from study date, whichever is the latest.

All concomitant medications will be listed, including verbatim descriptions and coded terms, and flags for prior/concomitant/post treatment medications. Prior, concomitant, and post treatment medications will be summarized using frequencies of subjects reporting each drug category and generic drug name. For each subject, multiple records of the same concomitant medication will be counted once within a drug class and generic drug name.

Summaries will also be produced for anti-cancer therapies (systemic therapy, radiotherapy as well as diagnostic and therapeutic procedures). These summaries will be created for ITT population and Week 24 population.

Table 6–1 Medication Classification

	Prior to study drug	Study drug started	Treatment with study drug	Study drug stopped	Follow up	Prior Medication?	Concomitant Medication?	Post-treatment Medication?
C1						Yes	No	No
C2						Yes	Yes	No
C3						No	Yes	Yes
C4						Yes	Yes	Yes
C5						No	No	Yes
C6						No	Yes	No
C7						No	Yes	No
C8						No	Yes	No

C1= medication started before study drug administration and ended on or before study drug administration

C2= medication started before study drug administration and ended during study drug administration
C3= medication started on or after study drug administration and ended after study drug administration
C4= medication started before study drug administration and ended after study drug administration
C5= medication started on or after study drug administration and ended after study drug administration
C6= medication started on or after study drug administration and ended before or on the same date as end of study drug administration
Note: C7 and C8 are covered under C6.

6.2 Efficacy

For Comparison 1, Arm A will be pooled with Arm C in the time-to-event analyses. Refer to censoring rules in Section 4.5 for the pooling algorithm. No pooling of Arm C subjects will occur in Comparison 1 for non-time-to-event endpoints (e.g. pain improvement rate).

As sensitivity analyses, the analyses described for Comparison 1 will also be performed between Arm A and Arm B only (i.e., without pooling Arm C data).

Each efficacy endpoint will be defined separately for Comparison 1 and Comparison 2. For Comparison 1 analyses, endpoints will be defined following randomization baseline. For Comparison 2 analyses, endpoints will be defined following Week 24 baseline (the 6th dose date) unless otherwise specified.

Imaging endpoints based on tumor assessments, will not follow the Week-24 baseline for Comparison 2 analyses. The study did not plan to do Week 24 re-baseline for the site investigators. The site investigators would determine PD only based on the randomization baseline. Once a subject had a PD (or a confirmed PD for bone progression) based on randomization baseline, the subject will not be further followed for a second PD using Week-24 assessment as the new baseline. Therefore, there will be no assessments after an observation of PD to perform re-reads of tumor assessments based on the Week-24 baseline by the central reviewer. This incomplete tumor assessments can lead to a biased analysis favoring one arm vs the other (i.e., the arm with more PDs based on randomization baseline could have more censored data for the analyses based on Week-24 baseline). Hence, the Comparison 2 analysis on the Week-24 population will only be performed based on the randomization baseline, not the Week-24 baseline for both investigator and centrally reviewed data.

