3.4 Determination of sample size

The sample size is based on two separate comparisons with no multiple-testing adjustment:

Comparison 1:

H01: $SSE-FS_{\text{high dose}} = SSE-FS_{\text{standard dose}}$, versus

HA1: $SSE-FS_{\text{high dose}} > SSE-FS_{\text{standard dose}}$.

This comparison will consider SSE-FS following randomization. Arm C subjects will be pooled with Arm A for the standard dose group. Refer to pooling algorithm in Section 4.5.2 and Censoring rules in Table 9–1.

Comparison 2:

H02: SSE-FS_{extended dose} = SSE-FS_{Standard dose}, versus

HA2: SSE-FS_{extended dose} > SSE-FS_{Standard dose}.

This comparison will include Arm A and Arm C subjects who received 6 or more doses.

The sample size calculations assume 30 subjects/month enrollment with 7 months ramp-up and a 3% loss to follow-up per month. The accrual period is anticipated to last approximately 16 months. Overall, 360 subjects are expected to be randomized at a 1:1:1 ratio. The primary endpoint cut-off, as defined in Section 3.3, is estimated to be reached in an average of 39.1 months.

- Comparison 1 assumes:
 - Arm A (standard dose) subjects have constant median SSE-FS of 9 months throughout the study
 - Arm C (extended dose) subjects have median SSE-FS of 9 months during the first 24 weeks of the study
 - Arm B (high dose) subjects have constant 50% improvement in SSE-FS (median 13.5, hazard ratio 0.667) .

Simulations indicated an average of 186.61 events would occur for this comparison at primary endpoint cut-off, and a 1-sided log-rank test with 0.10 significance gave approximately 90.5% power to test H01 versus HA1.

- Comparison 2 assumes:
 - Arm A (standard dose) subjects have constant median SSE-FS of 9 months
 - Arm C Extended dose subjects have
 - Median SSE-FS of 9 months for the first 24 weeks
 - A 65% improvement (median 14.85, hazard ratio 0.606) thereafter.

With 240 of 360 subjects randomized to Treatment Arm A and Treatment Arm C, simulations indicated that 44.65% of randomized subjects (107.2 of 240) would have a SSE-FS event or loss to follow-up during the first 24 weeks, leaving an estimated 55.35% (132.8) surviving SSE-free and eligible for inclusion at 24 weeks. An average of 74.91 simulated events occurred for this comparison, and a 1-sided log-rank test with 0.10 significance (0.2 for two-sided test) gave approximately 80.6% power to test H02 versus HA2.

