4.7 Additional Statistical Considerations

4.7.1 Delayed Effect Efficacy Assumptions

Since the comparison between the “standard” and “extended” regimens involves identical treatment for the first 6 doses, the following assumptions were made:

- Both regimens have identical efficacy for the first 6 doses, and
- The efficacy would diverge at the time that extended-dosing subjects received their 7th dose.

This feature is consistent with a delayed effect as described in Fine (2007) [1] and Zhang and Quan (2009) [2]. To account for this delayed-effect feature, hazards were modeled using a 2-compartment approach:

- With the standard (Arm A) and high-dose (Arm B) regimens having constant hazards throughout the study, and
- The extended regimen (Arm C) initially having the same hazards as the standard regimen (Arm A) but having a fixed change point at Week 24, approximately the point at which the 7th dose would begin, with constant, reduced hazards thereafter.

A sensitivity analysis using two-compartment Cox model will be performed by taking into account of this delayed-effect feature for Comparison 2. The details are specified in Section 6.2.1.

5. Analysis Sets

- **Intent-to-treat (ITT):** All randomized subjects. The ITT population will be used in the analysis of efficacy endpoints for Comparison 1. Subjects will be included in ITT analyses according to the treatment to which they were randomized as based on IXRS. The randomization baseline will be used in the ITT analyses.
- **Week 24(W24):** All ITT subjects in Arm A (standard dose) and Arm C (extended dosing) treated with radium-223 dichloride and eligible for further treatment at W24 (i.e., 7th injection). Week 24 applies to subjects who received the 6th injection without any dose delays. As dose delays are allowed per protocol, 6th injection can occur after Week 24 for subjects who had dose delays. Hence, this population is defined based on the number of injections not based on the timing. The W24 dataset

will be used for the analysis of efficacy endpoints related to Comparison 2 and associated evaluations. Subjects will be included in W24 analyses according to the treatment to which they were randomized.

- **Safety (SAF):** All subjects who have received at least one study drug administration. This safety population will be used in the analyses of all safety endpoints. Subjects will be included in the analyses according to the treatment they received.

6. Statistical Methodology

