6.2.2 Secondary Efficacy Analysis

6.2.2.1 Secondary efficacy endpoints

The secondary efficacy variables are specified below.

- Overall survival
- Time to first SSE
- Radiological progression-free Survival (rPFS)
- Time to radiological progression (TTP)
- Pain improvement rate
- Time to pain progression

Overall survival is defined for each comparison as the time (days) from the applicable start date to the date of death due to any cause. See [Table 9–3](#) in Appendix 9.1.2 for detailed censoring rules.

Comparison 1:

Arm C subjects who have died or are known to be alive after ‘pooling cut-off date’ will be censored on the ‘pooling cut-off’ date. Refer to Section 4.5 for pooling cut-off date.

All other subjects in arms A, B and C, refer to [Table 9–3](#) for censoring rules.

Overall Survival (OS) following randomization = End Date – Date of Randomization +1

Comparison 2:

For Comparison 2 eligible subjects, refer to [Table 9–3](#) for censoring rules.

Overall Survival (OS) following Week 24 baseline = End Date – Date of Week 24 baseline(the 6th dose date) +1

Time to first symptomatic skeletal event is defined for each comparison as the time (days) from the applicable start date to the date of the first SSE. See

[Table 9–4](#) in Appendix 9.1.3 for detailed censoring.

Time to radiological progression is defined for each comparison as the time (days) from the randomization date to the date of the first radiological progression. Comparison 2 will not follow the Week-24 baseline and randomization baseline will be used instead. See [Table 9–5](#) and [Table 9–6](#) in Appendix 9.1.4 for detailed censoring rules.

The central reviewer will evaluate the radiological imaging produced by the investigator. Primary radiological progression endpoints will be based on the central radiological reviewer assessments. Investigator assessments will be provided as a sensitivity analysis.

Radiological progression of soft-tissue disease is determined according to modified RECIST criteria, version 1.1 (See Protocol Section 14.1) based on MRI / CT scans of the chest, abdomen, and pelvis.

Radiological progression of bone disease is determined according to adapted PCWG2 criteria (see Protocol Section 14.2) based on whole body technetium-99 bone scans.

Radiological progression of bone disease requires confirmation. A subject is considered to have progressed by bone scan if:

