6.2.2.2 Analysis of secondary efficacy endpoints

The following secondary efficacy time-to-event endpoints will have hypothesis testing performed for both Comparison 1 and Comparison 2: OS, time to first SSE, time to radiological progression, and rPFS.

A one-sided type I error rate of 0.10 will be used for secondary efficacy endpoint hypothesis testing.

Hypothesis tests for these endpoints will be performed using a stratified log-rank test accounting for the same two randomization stratification factors as for the primary endpoint analysis (See Section 6.2.1). The treatment effect (hazard ratio) will be estimated using the Cox proportional hazards regression model stratified by the above-mentioned two randomization stratification factors. For rPFS and time to radiological progression, analyses will be done based on both the investigator's and the independent assessments. Analysis based on the independent central review assessment will be considered the primary analysis for rPFS.

Secondary efficacy time-to-event endpoints will be summarized using Kaplan-Meier [5] estimates. Median survival time together with the 25th and 75th percentiles and associated 80% and 95% Brookmeyer-Crowley [6] confidence intervals (CI) will be presented by group. Corresponding Kaplan-Meier [5] curves will be generated by group.

Pain improvement rate will be calculated for each post-baseline timepoint, with exact binomial 80% and 95% Clopper-Pearson [7] confidence intervals. Pain improvement rate with exact binomial 80% and 95% CIs will also be plotted by timepoint.

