9.1.5 Censoring rules for radiological progression-free survival (rPFS)

The following censoring rules will be used for both Comparison 1 and Comparison 2.

Table 9–7 Censoring for radiological progression-free survival following randomization

Situation	End Date	Censored	Reason for Censoring
No randomization baseline or post-randomization baseline radiological progression assessments	Date of Randomization	Yes	No baseline or post-baseline assessment.
Subject had a radiological assessment of PD following randomization (no 2 consecutive missing radiological assessments*)	Date of first radiological event	No	N/A
Death or PD immediately after two or more consecutive missed radiological assessments*	Date of last radiological assessment before missed assessments	Yes	Missed two or more consecutive tumor assessments
Subject discontinued from study for other than PD or death	Last radiological assessment date	Yes	Subject discontinued from study due to a reason other than PD or death
Death during the study (no 2 consecutive missing radiological assessments*) or before first radiological PD assessment	Date of Death	No	N/A
Subjects discontinued from study due to PD, but no documented date of PD	Date of last radiological assessment	Yes	Subjects discontinued from study due to PD, but no documented date of PD
Subject still on study at the time of data cutoff without PD	Last radiological assessment before data cutoff	Yes	Subject is still alive without PD
New non-protocol permitted systemic anti-cancer treatment started	Date of last radiological assessment before starting new systemic anti-cancer treatment	Yes	New systemic anti-cancer treatment started

*Two consecutive missing radiological assessments are defined as the time interval between two consecutive radiological assessments is more than 28 weeks = $2 \times (12+2)$ week, where 12-week is scheduled frequency for tumor assessment and 2-week is protocol-allowed window

Radiological progression date and status mentioned in above table will be obtained following the rules specified in [Table 9–6](#).

rPFS following randomization = End date – randomization date +1.

There will be no Week 24 baseline censoring for Comparison 2. Randomization baseline will be used for Comparison 2.

In addition to the rules in [Table 9–7](#), the following rule will be applied to Comparison 1:

Situation	End Date	Censored	Reason for Censoring

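### Comparison 2 times radiological progression and rPFS from randomization, so progressions dated before the 6th dose count as events and dilute the comparison of extended with standard dosing

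*SAP*

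**What the plan says.** Comparison 2 uses the W24 set: Arm A and Arm C subjects defined by number of injections and eligible for further treatment (section 5). Section 4.7.1 assumes equal efficacy over the first six doses and adds: "The efficacy would diverge at the time that extended-dosing subjects received their 7th dose".

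The default time origin for Comparison 2 is the 6th dose date (sections 4.5.1 and 6.2). SSE-FS, OS, time to first SSE and time to pain progression follow it. For all of these except OS, where the question cannot arise, a subject with an earlier event is censored at that date (Table 9-2; section 9.1.3).

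The two secondary imaging endpoints do not follow it. Section 6.2 says of imaging endpoints: "Hence, the Comparison 2 analysis on the Week-24 population will only be performed based on the randomization baseline, not the Week-24 baseline". For time to radiological progression, section 6.2.2.1 says "Comparison 2 will not follow the Week-24 baseline and randomization baseline will be used instead". For rPFS, section 9.1.5 says "There will be no Week 24 baseline censoring for Comparison 2. Randomization baseline will be used for Comparison 2". Section 9.1.4 has the same no-censoring sentence.

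Both endpoints are formally tested. Section 6.2.2.2 reads "The following secondary efficacy time-to-event endpoints will have hypothesis testing performed for both Comparison 1 and Comparison 2", with both on the list that follows, and "A one-sided type I error rate of 0.10 will be used for secondary efficacy endpoint hypothesis testing".

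The reason in section 6.2 is that sites judged progression only against the randomization scan and stopped following a subject for progression after the first one. Re-reads against a Week 24 reference scan would therefore be incomplete, and possibly unequally so between arms.

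**The concern.** Three choices are bundled into one: the scan against which progression is judged, the date the clock starts, and who is at risk at that date. The SAP's reason settles the first. It does not bear on the other two. Progression can remain defined against the randomization scan while time is counted from the 6th dose among subjects who have not yet progressed. That needs no scan after progression, so the bias that section 6.2 fears does not arise.

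As written, a progression dated in the shared six-dose period is an event that extended dosing could not have influenced. No subject in this set can die before dose 6, so that stretch of rPFS is also death-free by selection, which lengthens the medians in both arms.

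The SAP recognises the mechanism elsewhere. Section 4.5.1 warns that using the 6th rather than the 7th dose date may dilute the Arm C effect somewhat; randomization lies about 20 weeks earlier still. For SSE-FS, section 6.2.1 makes the from-randomization analysis of Comparison 2 supportive only and adds a 2-compartment Cox model split at the 6th dose. The SAP states neither safeguard for the imaging endpoints. At stake is whether a null imaging result in Comparison 2 could be read as saying anything about extended dosing.

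**Working it through.** **Reproducing the SAP's figure.** The SAP gives no power for the imaging endpoints, so the check starts from SSE-FS2. Section 3.4 says "An average of 74.91 simulated events occurred for this comparison, and a 1-sided log-rank test with 0.10 significance" "gave approximately 80.6% power to test H02 versus HA2", at a hazard ratio of 0.606 and 1:1 allocation.

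Power = Φ(|ln HR| × √(D/4) − 1.2816). With D = 74.91: 0.5009 × 4.328 − 1.282 = 0.886, so power is 81.2% against 80.6% stated. The W24 count also reproduces: 24 weeks is 5.52 months, and 0.5^(5.52/9) × 0.97^5.52 = 55.3%, or 132.6 of 240 against 132.8 stated.

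**Dilution in closed form.** Let p be the share of events in the shared period (HR 1), with HR 0.606 afterwards. From randomization, the average log HR is (1 − p) × ln 0.606 on D events. From the 6th dose it is ln 0.606 on D(1 − p) events. D = 75 is borrowed from SSE-FS2, and p is assumed because the SAP does not give it. For p = 30%, from randomization: 0.3506 × √(75/4) − 1.282 = 0.237, power 59%. From dose 6: 0.5009 × √(52.5/4) − 1.282 = 0.533, power 70%.

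| p | HR from randomization | Power from randomization | Power from dose 6 (HR 0.606) |
|---|---|---|---|
| 10% | 0.64 | 75% | 78% |
| 20% | 0.67 | 68% | 75% |
| 30% | 0.70 | 59% | 70% |
| 40% | 0.74 | 51% | 66% |
| 50% | 0.78 | 42% | 60% |

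**Simulation of rPFS.** From the SAP: 133 W24 subjects, HR 0.606 after Week 24 (the SSE-FS effect, borrowed and applied to progression and death), 3% monthly loss, one-sided 0.10 log-rank test, and scans at Weeks 8, 16, 24 and every 12 weeks after (the schedule in section 6.2.3.1.1 for quantitative bone scans). Assumed: median time to progression 4, 6, 9 or 12 months; median survival 12 months from dose 6; dose 6 at Week 20; and a share of subjects with progression at Week 8 or 16 who still reach dose 6. There were 4,000 replicates per row.

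| Share reaching dose 6 | Progression median (months) | Events before dose 6 / all | HR, randomization vs dose 6 | Power, randomization vs dose 6 |
|---|---|---|---|---|
| 100% | 4 | 63 / 123 | 0.84 vs 0.69 | 33% vs 46% |
| 100% | 6 | 46 / 117 | 0.80 vs 0.68 | 43% vs 58% |
| 100% | 9 | 33 / 111 | 0.75 vs 0.66 | 54% vs 64% |
| 100% | 12 | 25 / 106 | 0.73 vs 0.66 | 59% vs 67% |
| 30% | 4 | 28 / 118 | 0.77 vs 0.70 | 47% vs 57% |
| 30% | 6 | 18 / 112 | 0.72 vs 0.67 | 61% vs 67% |
| 30% | 9 | 12 / 106 | 0.70 vs 0.66 | 68% vs 72% |
| 30% | 12 | 9 / 102 | 0.68 vs 0.66 | 70% vs 73% |
| 10% | 4 | 11 / 115 | 0.72 vs 0.69 | 59% vs 63% |
| 10% | 6 | 7 / 110 | 0.69 vs 0.67 | 68% vs 70% |
| 10% | 9 | 4 / 104 | 0.68 vs 0.67 | 71% vs 72% |
| 10% | 12 | 3 / 100 | 0.66 vs 0.65 | 74% vs 75% |

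Shorter runs of the same set-up gave gains of 5 to 14, 2 to 9 and 0 to 5 points for the three shares. The dose-6 hazard ratio stays above 0.606 because the effect is assumed to start at Week 24, four weeks after the clock.

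**Type I error.** With HR 1 throughout and all early progressors reaching dose 6, the from-randomization test rejected in 10.6% (4-month median) and 10.3% (12-month median) of replicates, against a nominal 10%.

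**The case against.** The strongest objection is that the dilution may be small. The simulation's first block assumes progression never prevents a subject reaching dose 6. The W24 set also requires eligibility for further treatment, and the treatment rules belong to the protocol, which is not at hand. If few early progressors reach dose 6, little is lost. This stands, and it is why the 100% rows are an upper bound.

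It does not remove the point. Bone progression needs a confirming scan at least 6 weeks later and is dated to the first scan (section 6.2.2.1). With scans at Weeks 16 and 24 and 4-weekly dosing, a bone progression first seen at Week 16 would be confirmed at about Week 24, after dose 6 at about Week 20. The event date then precedes dose 6. A bone progression first seen at Week 8 does not count automatically, since confirmation there requires at least two further new lesions. Neither this rule nor censoring at new anti-cancer treatment is modelled.

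A reader might infer from section 6.2 that the SAP itself expects early progressors in the W24 set, because it mentions one arm having more progressions. That remark gives no timing and fits progressions after Week 24 equally well. A reader might also infer a biased or invalid test. The documents do not support that: under the SAP's own assumption, shared-period events arise alike in both arms.

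Finally, the choice was disclosed and reasoned (section 6.2; Table 7-1). That is so, but the reason concerns only the reference scan.

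**Conclusion.** The point holds as a loss of efficiency and a blurred question on two tested secondary endpoints. Progressions dated before the 6th dose count in Comparison 2, move the hazard ratio toward 1 and lower power. Type I error is not inflated, and SSE-FS2 and OS, which start at the 6th dose, are untouched.

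The size cannot be fixed from the SAP, which gives no rate of progression before dose 6. Under the assumptions above, the gain in rPFS power from starting at the 6th dose is about 5 to 14 points if all early progressors reach dose 6, about 3 to 6 points (up to 10 at the 4-month median) if 30% do, and 0 to 5 points if 10% do. The 6th-dose origin did not lose power in any scenario, although it uses fewer events. The change is worth making because it is cheap, not because the loss is known to be large.

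**What to change.** In sections 6.2, 6.2.2.1, 9.1.4 and 9.1.5, for Comparison 2 only:

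- Keep progression judged against the randomization scan.
- Start time to radiological progression and rPFS at the 6th dose date, and make this the tested analysis.
- State one rule for early progressions: a subject whose progression, dated by first observation under section 6.2.2.1, falls on or before the 6th dose date is censored at that date, as Table 9-2 does for SSEs. Such a subject adds no event, including any later death in rPFS.
- Replace the sentences in 9.1.4 and 9.1.5 that rule out Week 24 censoring. Table 9-5 also serves the exploratory bone and soft-tissue endpoints, so say that the change is limited to the two secondary endpoints.
- Keep the from-randomization analysis as supportive, as section 6.2.1 does for SSE-FS.
- Add the 2-compartment Cox model, split at the 6th dose, as a sensitivity analysis for both endpoints.

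The cost is SAP wording, one derived start date and one censoring rule, with no new reads or visits. There are two drawbacks. Subjects already progressed at dose 6 contribute nothing, which is a further post-randomization selection on top of the W24 set. A few bone progressions first seen before dose 6 will be classified using a confirming scan that may fall after dose 7, when the arms differ; the Cox model is there to show whether that matters.
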